# Registration and reporting of suspected adverse events

Any unexpected and serious side effects and suspected adverse reactions will be immediately reported to the project leader as well as the trial data and safety monitoring board.

#### 7. Trial start date

April 2018 with initial expected completion by Q4 2019.

AMENDMENT: Due to reorganisation of abortion care in the Stockholm region with closure of SESAM clinic at Karolinska and initial gradual but then total change to central telephone booking and the outbreak of covid-19 the project has been phased with constant delays. The time has been used to adjust logistics and for piloting the study tools, and development of the study website and database.

First patient recruited in actual trial after logistic adjustments April 29, 2020. Estimated completion Q4 2022 New trial sites added for standard care patients; Södersjukhuset, Danderyds hospital and Ultragyn.

### 8. Statistical analysis plan; power calculations - sample size

Sample size

The hypothesis to test is a non-inferiority hypothesis. The aim is to prove that telemedicine counseling is not inferior compared to standard abortion treatment. The expected efficacy rate (primary outcome) is 97.5% in both groups. The non-inferiority margin is set at 3%. The primary hypothesis will be tested by constructing a 95% confidence interval (CI) for the difference between the two treatments (intervention-control). If the upper limit of the CI is less than 3% the intervention will be declared as non-inferior to standard abortion care. In total 635 patients per group (1370 in total) is needed to obtain a power of 90%. To compensate for a 10% loss to FU an additional 138 women will be added to include 754 patients per group (total 1508 women).

Numbers and proportions of women having failed abortion and surgical intervention for incomplete abortion will be calculated by intervention. Both interventions will be compared using both absolute and relative measures with 95% confidence intervals. An intention-to-treat analysis as well as a per-protocol analysis will be performed. To evaluate the differences between the groups regarding independent nominal data such as side-effects and compliance, the chi squared test will be used. Continuous variables with a normal distribution, will be analysed using the Student's t-test whereas variable which are not normally distributed, such as age, GA (self-estimate vs LMP vs US) will presented as medians (range) and compared using Mann-Whitney U-test. Discrete numerical variables such as parity and bleeding days will be presented as means (range) and assessed for normality and comparison using the t-test or the Mann-Whitney U-test. Numeric variables (time lost from work and number of unplanned visits/consultations) will be analysed using analysis t-test. Results will be considered statistically

significant if P-value < 0.05. An independent data and safety monitoring committee will evaluate AE/SAE and make decisions if the trial should be stopped or continue as planned. Reason for stopping the trial could be a high failure rate or low acceptability rate in the intervention group. The plan for analysis and the study protocol has been developed in collaboration with prof. [name], Statisticon AB.

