### 4. Outcome measures

# Primary outcome

Efficacy of medical abortion defined as complete abortion without ongoing intrauterine pregnancy or surgical intervention for incomplete abortion within 30 days of the abortion treatment. The outcome will be determined based on the home low sensitivity uhCG and patient records (surgical intervention).

Secondary outcomes will include safety (AE/SAE), any additional medical treatment of incomplete abortion, bleeding days and estimated amount, infection, surgical treatment for other indications than ongoing pregnancy or incomplete abortion, unscheduled contacts and visits, acceptability with the abortion counselling and treatment (in-clinic or self managed, self reported /estimated gestational length and contraceptive choice.

Incomplete abortion will be defined as products of conception remaining in the uterus with continued bleeding, bulky uterus, and open cervix at examination, possibly necessitating surgical evacuation at the discretion of the provider or at the woman's request derived from patient records.

Adverse events (AEs) will be recorded. The completeness of the abortion and any AEs will be identified by the on line follow up and by clinical examination.

Data management will be organized locally by data entry personnel and at the WHO centre, Karolinska. Data will be entered by use of a clinical trial software, checked for accuracy, and corrected after consultation of clinical records and research assistants, and reviewed monthly by the Study Coordinator at the WHO centre with further checking of clinic records as necessary.

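### The non-inferiority rule checks the wrong confidence limit for an efficacy outcome and, as written, sets no bound on how much worse telemedicine may be

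*Combined protocol and SAP*

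**What the plan says.** The section on the primary outcome defines a success measure: "Efficacy of medical abortion defined as complete abortion without ongoing intrauterine pregnancy or surgical intervention for incomplete abortion within 30 days" of treatment. Section 8 (statistical analysis plan and sample size) keeps that scale: "The expected efficacy rate (primary outcome) is 97.5% in both groups". On the margin it says "The non-inferiority margin is set at 3" per cent, with no sign and no scale. The test is a "95% confidence interval (CI) for the difference between the two treatments (intervention-control"), and the decision rule is "If the upper limit of the CI is less than 3% the intervention will be declared as non-inferior to standard abortion care".

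Nowhere does the document refer to a lower limit or to −3%, or say that the primary interval is for failure rates.

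**The concern.** Three elements fix the meaning of the rule: the outcome (higher is better), the direction of subtraction (intervention minus control) and the limit tested (upper, against +3%). Taken together they point the wrong way. If telemedicine is worse, the difference is negative and the upper limit moves further below +3%, so the criterion becomes easier to meet as the arm gets worse. If telemedicine is better, the upper limit moves towards +3% and the criterion becomes harder to meet.

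This is the only criterion given for the trial's main claim. Read literally, it does not control the chance of calling an inferior service non-inferior.

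**Working it through.** **Inputs.** From section 8: efficacy 97.5% in both arms, margin 3 points, two-sided 95% interval (one-sided 2.5%), power 90%, 635 per group before and 754 per group after the allowance for loss to follow-up. Assumed here: 1:1 allocation and an unpooled Wald interval, since the plan names no interval method.

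**The plan's own sample size.** Section 8 states: "In total 635 patients per group (1370 in total) is needed to obtain a power of 90" per cent. The usual formula gives

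n = 2 × 0.975 × 0.025 × (1.960 + 1.282)² / 0.03² = 569.2, so 570 per group.

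With the continuity correction,

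n = (569.2/4) × [1 + √(1 + 4/(569.2 × 0.03))]² = 634.1, so 635 per group.

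This reproduces the plan's 635. The formula uses p(1−p), which is the same for success and failure, and assumes a true difference of zero. It therefore cannot show which scale or which limit was intended.

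**Chance of declaring non-inferiority.** Let p_T and p_C be the true efficacies, d = p_T − p_C and SE = √[p_T(1−p_T)/n + p_C(1−p_C)/n].

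- Rule as written (upper limit < +3%): Φ((0.03 − d)/SE − 1.96)
- Lower-limit rule (lower limit > −3%): Φ((d + 0.03)/SE − 1.96)

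Example at p_T = 94.5%, p_C = 97.5%, n = 635: SE = √[(0.051975 + 0.024375)/635] = 0.01097. As written: Φ(0.06/0.01097 − 1.96) = Φ(3.51) = 99.98%. Lower limit: Φ(0 − 1.96) = 2.5%.

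Results with control efficacy at 97.5%:

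| True telemedicine efficacy | d (points) | As written, n = 635 | Lower limit, n = 635 | As written, n = 754 | Lower limit, n = 754 |
|---|---|---|---|---|---|
| 99.5% | +2.0 | 31.2% | ~100% | 36.0% | ~100% |
| 99.0% | +1.5 | 53.3% | ~100% | 60.4% | ~100% |
| 97.5% | 0 | 92.8% | 92.8% | 96.2% | 96.2% |
| 96.0% | −1.5 | 99.5% | 32.6% | 99.9% | 37.6% |
| 94.5% | −3.0 | 99.98% | 2.5% | 99.997% | 2.5% |
| 90.0% | −7.5 | ~100% | ~0% | ~100% | ~0% |
| 87.5% | −10.0 | ~100% | ~0% | ~100% | ~0% |

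Binomial simulation (400,000 trials per scenario) agrees. At 635 per arm, as written and lower limit respectively: 92.6% and 92.6% with equal arms; 99.99% and 3.0% at 94.5%; 100% and 0% at 90.0%. In the same runs, an upper limit below 3% for the difference in failure rates gave the same results as the lower-limit rule on efficacy.

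**One data set.** Observed 90.0% against 97.5% with 635 per arm: d = −7.5 points, SE = √[(0.09 + 0.024375)/635] = 0.01342, 95% CI −10.1 to −4.9. The whole interval lies below −3 points. The upper limit, −4.9, is below +3, so the written rule declares non-inferiority.

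**The case against.** The strongest reply is that the sponsor meant failure rates. The sentence on the interval speaks of a difference between treatments without repeating the word efficacy. On a failure scale, intervention minus control with an upper limit below 3% is correct in sign, direction and limit. The next paragraph of section 8 tabulates failed abortions and surgical interventions for incomplete abortion by arm, which together are the complement of the primary outcome, and compares the arms with 95% intervals. The stated aim of showing that telemedicine is not inferior also makes it unlikely that anyone would defend a non-inferiority claim on an interval of −10 to −5 points.

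This makes a slip in wording or scale the likely origin, but it does not rescue the text. The only rate given before the rule is efficacy, labelled as the primary outcome, and the failure tabulation is never tied to the margin or to the primary interval. The reader has to supply the scale.

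A second objection concerns size when telemedicine is better. At the planned control rate of 97.5% the advantage cannot exceed 2.5 points, so the written rule does not always fail. In simulation at 685 per arm it passes about 74% of the time at 98.5%, 57% at 99.0% and 19% at 100%. A pass rate as low as about 3% needs a case such as 99% against 96%, and that control rate is an assumption not found in the plan. The 685 is also an assumption: it is half of the printed total of 1370, whereas 2 × 635 = 1270. This part of the objection stands as a limit on the size of the effect for a better arm. It leaves the worse-arm results untouched, and these hold at 635, 685 and 754 per arm.

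**Conclusion.** The decision rule is wrong as written for the outcome it is attached to. At a true deficit equal to the margin, it declares non-inferiority about 99.98% of the time where 2.5% is intended, and for larger deficits practically always. It also penalises a better telemedicine arm, passing about 53% of the time at 99.0% against 97.5% (635 per arm), where the lower-limit rule passes almost always. These figures rest on reading the difference as one in efficacy, on independent binomial outcomes with 97.5% control efficacy, and on a Wald interval.

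If failure rates were intended, the rule itself is sound, but the plan still omits the scale of its primary comparison. Two analysts could then reach opposite conclusions from the same data. The section on the randomization procedure says that the study is not masked, which is a further reason not to leave the scale to be settled once results are known. The correction must be made under either reading.

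**What to change.** Replace the rule in section 8 with one of these, and use the same scale for the margin, the primary interval, and both the intention-to-treat and per-protocol analyses:

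- *Efficacy scale:* non-inferiority is declared if the lower limit of the two-sided 95% confidence interval for the difference in efficacy (intervention minus control) is greater than −3 percentage points.
- *Failure scale:* non-inferiority is declared if the upper limit of the two-sided 95% confidence interval for the difference in failure proportions (intervention minus control) is less than 3 percentage points, where failure is the complement of the primary efficacy outcome.

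The first is closer to the rest of the document, which states the outcome and the expected rate as efficacy. The change should be dated and made before outcomes are compared by arm. It costs one sentence. It needs no new data or participants, and the calculated 635 per group is unaffected because equal rates are assumed and the variance is the same on both scales.

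### The sample size statement contradicts itself: 635 per group makes 1270 women, not 1370, and the enrolment target of 1508 is built on 1370

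*Combined protocol and SAP*

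**What the plan says.** All the figures are in section 8 of the combined protocol and SAP (statistical analysis plan; power calculations - sample size).

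- Inputs: "The expected efficacy rate (primary outcome) is 97.5% in both groups. The non-inferiority margin is set at 3" per cent. Non-inferiority is "tested by constructing a 95% confidence interval (CI) for the difference between the two treatments".
- Evaluable number: "In total 635 patients per group (1370 in total) is needed to obtain a power of 90" per cent.
- Enrolment target: "To compensate for a 10% loss to FU an additional 138 women will be added to include 754 patients per group (total 1508 women").

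The design has two groups, and 754 per group against 1508 in total shows that they are equal in size. No formula or software is named for the calculation. No other section gives a sample size.

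**The concern.** The per-group number and the total in one sentence cannot both be right, and the following sentence carries the total forward into the recruitment target. This makes it more than a stray digit in a number that nothing depends on.

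The evaluable number is the yardstick for whether a non-inferiority trial reached its planned information. Here the plan offers two yardsticks, 1270 and 1370. A trial that recruits 1508 women and loses exactly the expected 10% would pass the first and narrowly miss the second. The section on the trial start date reports long delays, the closure of the original clinic and added sites, so whether enough women have been recruited is a practical question.

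**Working it through.** **1. The totals**

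- 2 × 635 = 1270, which is 100 below 1370.
- 1370 / 2 = 685, which is 50 above 635.

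**2. Which figure the target uses**

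| Step | From 685 per group | From 635 per group |
|---|---|---|
| Total evaluable | 1370 | 1270 |
| Add 138 | 1508 | 1408 |
| Per-group number × 1.10 | 753.5, rounded up to 754 | 698.5, rounded up to 699 |
| Resulting total | 1508 | 1398 |
| Women to add to reach 1508 | 138 | 238 |

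The plan's 138, 754 and 1508 all come from the 685 column.

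**3. Which figure the inputs support**

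Inputs from section 8: p = 0.975 in both groups, margin d = 0.03, two-sided 95% interval (z = 1.960), 90% power (z = 1.2816).

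- *Normal approximation, uncorrected.* n = 2p(1 − p)(1.960 + 1.2816)² / d² = 2 × 0.975 × 0.025 × 10.507 / 0.0009 = 569.2, so 570 per group.
- *With continuity correction.* N = (n/4) × [1 + √(1 + 4/(n·d))]² = (569.15/4) × (1 + 1.1110)² = 634.1, so **635 per group**. This reproduces the plan's per-group figure.
- *Farrington-Manning.* With restricted rates of 0.9531 and 0.9831 the result is 655.6, so 656 per group.

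None of the three gives 685. For the continuity-corrected formula to give 685 at 90% power, the common efficacy would have to be about 97.3% (p = 0.9727), not 97.5%.

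**4. What 1508 delivers**

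1508 × 0.90 = 1357.2, or 678 whole women per group: 43 more than 635 and 7 fewer than 685. The total is 13 below 1370 because adding 10% does not fully offset a 10% loss.

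Continuity-corrected power is Φ[(0.03 − 1/N) / √(2p(1 − p)/N) − 1.96] with p = 0.975:

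| N per group | Power |
|---|---|
| 635 | 90.0% |
| 678 | 92.0% |
| 685 | 92.3% |

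**The case against.** The strongest reply is that this is one wrong digit with no consequence. If 635 is read as 685, everything after it falls into place: 685 doubles to 1370, 10% more is 754, and 754 doubles to 1508. The operative target of 1508 is stated once, is internally consistent, and after 10% loss exceeds 570, 635 and 656 per group.

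The last part stands, and it limits the point to consistency. The single-digit explanation is possible but not established. 635 is exactly what a standard formula gives from the stated inputs, which would be a notable coincidence for a slip, and it leaves 685 without a derivation.

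A second reply is that three formulas do not exhaust the options, since the plan names no interval method. That is fair. Exact enumeration with the ordinary Newcombe interval gives 90.3% power at 635, so 635 is not unique to the continuity-corrected formula. With the continuity-corrected Newcombe interval, power is 89.5% at 656 and 90.9% at 685, so a stricter method needs more than 656. But that method already gives 90.4% at 678, so it does not yield 685 as the requirement either. The supportable statement is that no method tried produces 685, not that none could.

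**Conclusion.** The point holds. The per-group number and the total in section 8 differ by 100 women, and the enrolment target rests on the one that the stated inputs do not reproduce. The arithmetic in steps 1 and 2 needs no assumption beyond two equal groups. Attributing 635 to a continuity-corrected formula is an inference from an exact match.

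The text alone does not settle which number was intended; only the original calculation can. The trial is not underpowered at its stated assumptions of 97.5% efficacy and 10% loss. This is a plain error in the central sample size statement that should be corrected, but it does not threaten the conclusion.

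**What to change.** Check the original calculation, name the formula, and restate one chain: inputs, evaluable number per group, total, allowance for loss, enrolment target.

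- **If 635 is confirmed:** state 1270 evaluable women. Then either keep 1508 and say that it leaves about 678 per group after 10% loss (about 92% power if the formula is the continuity-corrected one), or restate the target as 1270 / 0.90 = 1411.1, so 1412 (706 per group). The second option divides by 0.90, whereas the plan appears to multiply by 1.10, so the convention should be stated. Keeping 1508 is the simpler course.
- **If 685 was intended:** correct the per-group figure and give the inputs or method that produce it. Also note that 1508 less 10% is 1357, or 13 below 1370. Dividing by 0.90 would give 762 per group (1524), 16 more than planned, so the plan should say whether the small shortfall is accepted.

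The cost is a look at the original calculation and one corrected sentence. The margin and the analysis do not change. No extra women are needed if 635 is confirmed, or if the small shortfall against 685 is accepted.

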### 2. Participants

Women requesting medical termination of pregnancy with home administration of misoprostol and home self-assessment of outcome of treatment, with pregnancies up to 63 days gestation (based on ultrasound dating).

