### 3. Interventions

Women with an unwanted pregnancy, with no contraindication to medical abortion and self administration of misoprostol at home, of up to 63 days gestation, will be randomised into two groups at the time of the telephone booking:

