# 5. Eligibility criteria

*Inclusion criteria:* Women 18 years old and above, requesting termination of pregnancy by means of mifepristone followed by home administration of misoprostol at < /=63 days of gestation, with no contraindication to medical abortion and self administration of misoprostol at home, and who have given their informed consent will be eligible for study recruitment.

Exclusion criteria: Women who do not wish to participate, women who do not want home administration of misoprostol, women who are unable to communicate in Swedish, or English, and women with symptoms and signs of ectopic pregnancy. Minors (i.e. women < 18 years of age) will not be enrolled in the study. Women seeking termination of pregnancy with no visible intrauterine pregnancy.

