### Website

Women randomised to Group 1 (telemedicine counselling) will receive the address to a designated website. The content of counselling will include eligibility criteria, information regarding the treatment course, expected effects, side effects and signs and symptoms of complications. All women will also receive contact information to a help desk and information on when and where to contact in case of need.

Women randomised to study Group 1 will receive an appointment for an ultrasound scan, mifepristone treatment, chlamydia test and pick up of study medication. A nurse midwife/doctor will be responsible for the ultrasound scan to confirm intrauterine pregnancy and gestational length. Following the ultrasound scan mifepristone will be swallowed in the clinic according to the Swedish law. No further abortion counselling will be provided at this visit. However contraceptive counselling and prescription is provided as needed.

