### Randomization procedure

Randomization: We will use a computer-generated randomization scheme with a varying block size. Randomization will be performed :1 by a midwife in the abortion clinic at the time of the first telephone consultation after the patient has been judged eligible for participation and has given her oral informed consent. Allocation to study group will be done after completion of a checklist of inclusion and exclusion criteria by opening consecutively numbered opaque, sealed, envelopes containing the randomisation group for each participant. Women will be identified through a patient log.

Women will be randomly assigned to either Group I) telemdicine counselling or Group II) standard face-to-face counselling. Women in group I will be given the address to a designated website and an appointment for ultrasound scan and pick up of medication while women in group II will be given an appointment to the abortion clinic. Medical abortion will be performed according to the Swedish national guidelines. Women will receive mifepristone (LinePharma, Paris, France) 200 mg orally at the clinic (counts as Day 1). Twenty-four to 48 hours later women self-administer 800 mcg misoprostol vaginally or sublingually (4 tabl Cytotec® 200 mcg, Pfizer, New York, USA). If bleeding has not started or is scant women will be advised to administer a second dose of 400mcg misoprostol sublingually 3 hours later. Follow-up will be done 2 weeks after treatment and outcome of abortion assessed primarily by low sensitivity urinary hCG test. The study will not be masked.

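### Women are randomised by telephone before the ultrasound: do the undefined intention-to-treat and per-protocol sets put the non-inferiority verdict at risk?

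*Combined protocol and SAP*

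**What the plan says.** Under 3. Interventions, women "will be randomised into two groups at the time of the telephone booking". The Randomization procedure section puts allocation "at the time of the first telephone consultation after the patient has been judged eligible for participation and has given her oral informed consent", after a checklist of the entry criteria.

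Two of those criteria depend on the later clinic visit. Section 2 dates the 63-day limit by ultrasound. Section 5 excludes "Women seeking termination of pregnancy with no visible intrauterine pregnancy". In the telemedicine group the visit is where this is settled (Website section): "A nurse midwife/doctor will be responsible for the ultrasound scan to confirm intrauterine pregnancy and gestational length". Section 3 places ultrasound dating for the control group at its clinic appointment. Consent is taken again online and at the visit (Enrolment), mifepristone follows the scan, the study is not masked, and women may withdraw at any time (Discontinuation).

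Section 4 times the primary outcome over 30 days from the abortion treatment. On analysis sets, section 8 has one sentence: "An intention-to-treat analysis as well as a per-protocol analysis will be performed". Its decision rule is "If the upper limit of the CI is less than 3% the intervention will be declared as non-inferior to standard abortion care", with no set named. On numbers it says "To compensate for a 10% loss to FU an additional 138 women will be added", giving 754 per group.

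**The concern.** The design is bound to produce randomised women who turn out to be ineligible, do not attend, or leave before mifepristone. The primary outcome has no natural value for them, and the plan does not say how they are counted.

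Three rules are conceivable, and they behave differently in a non-inferiority comparison:

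- Counting these women as failures in both groups adds noise and can hide true non-inferiority.
- Counting them as successes dilutes a real deficit and makes a false claim easier.
- Leaving them out keeps the comparison clean, but the exclusion comes after open allocation and could differ by group.

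With two analyses named, neither defined and neither ranked, a disagreement between them would leave the conclusion to be chosen after the data are seen.

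**Working it through.** **Inputs from section 8.** Efficacy is 97.5% in both groups, the margin is 3 points, the two-sided 95% interval means one-sided 2.5%, power is 90%, with 635 per group before loss, 10% loss, and 754 per group enrolled. The criterion is read as the upper limit of the difference in failure rates (intervention minus control) lying below 3 points. The printed total of 1370 is not twice 635 (2 × 635 = 1270). That is a separate slip, and 754 is used as it stands.

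**The plan's own figure.** n = 2 × 0.975 × 0.025 × (1.960 + 1.282)² / 0.03² = 569.2 per group. With a continuity correction, (569.2/4) × [1 + √(1 + 4/(569.2 × 0.03))]² = 634.1, rounded up to 635. The plan's number is therefore matched by the continuity-corrected method, and both versions are shown below.

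**Which denominator do the plan's figures fit?**

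- If an assumed 5% were untreated and scored as failures, expected efficacy would be 0.975 × 0.95 = 92.6%, not 97.5%.
- If the planned 10% loss were scored as failures, it would be 0.975 × 0.90 = 87.75%.
- Enlarging the sample for loss makes sense only if lost women leave the denominator.
- The Variables and measures section records each abortion as complete, incomplete or failed, which presupposes treatment.

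The plan's figures therefore describe treated women with an outcome.

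**Power on that reading.** Power = Φ(0.03/√(2p(1−p)/n) − 1.96). For the corrected version, n is replaced by (n − 1/0.03)²/n. After 10% loss, n = 754 × 0.9 = 678.6. With a share u untreated and excluded, n = 678.6(1 − u). Every u is an assumption, equal in both groups.

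| u | n per group | corrected | uncorrected |
|---|---|---|---|
| 0 | 679 | 92.0% | 94.3% |
| 2% | 665 | 91.4% | 93.9% |
| 5% | 645 | 90.5% | 93.2% |
| 10% | 611 | 88.8% | 91.9% |

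For u = 5%, uncorrected: √(2 × 0.975 × 0.025/645) = 0.00869, 0.03/0.00869 − 1.96 = 1.49, and Φ(1.49) = 93.2%. Power drops below 90% at about 6.5% untreated (corrected) or 16% (uncorrected).

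**Untreated women scored as failures.** Put p = 0.975(1 − u) with n = 678.6. Power is 72% corrected and 76% uncorrected at u = 2%, and 52% and 56% at u = 5%.

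**Untreated women scored as successes.** Take a true 3-point deficit in treated women (97.5% against 94.5%) and 754 per group with no other loss. At u = 5% the rates become 97.625% and 94.775%, a difference of 2.85 points with standard error 0.00982. Then Φ((0.03 − 0.0285)/0.00982 − 1.96) = 3.5%, against the nominal 2.5%. It is 2.9% at u = 2% and 5.0% at u = 10%.

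**How often would two analyses disagree?** This used 400,000 simulated trials with 2.5% true failure in both groups and uncorrected intervals.

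| Compared with treated women | u = 2% | u = 5% |
|---|---|---|
| Per-protocol set dropping a further 5% to 10% at random | about 3% to 4% | about 3% to 5% |
| All randomised, untreated as failures | 19% | 38% |
| All randomised, untreated as successes | 0.7% | 2.0% |

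**The case for a change.** The strongest case for a change is that a non-inferiority trial should fix its deciding analysis before the data are seen, that writing it down costs only a few sentences, and that the extremes are far apart. With 10% of 754 lacking an outcome, uncorrected power is about 94% if they are left out and about 43% if they count as failures in an all-randomised analysis. The telephone checklist cannot supply an ultrasound date. Section 6 invokes CONSORT for non-inferiority trials, but the plan still defines no sets.

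Much of this stands: the sets are undefined, no priority is given, and a short definition would be tidier. It does not show that the plan would mislead. The 43%, the 52% to 76% and the 19% and 38% all need a woman found ineligible at ultrasound, not attending or lost to follow-up to be scored as a failed abortion. No passage suggests that, and it contradicts the 97.5% on which the trial is sized.

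Requiring non-inferiority in both sets is a matter of preference, since one named set would serve as well, and it has a price. At 2% or 5% untreated, a per-protocol set that drops a further 5% to 10% has 580 to 632 women per group. By the continuity-corrected method its test alone has 87.0% to 89.9% power, below the target.

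Unequal exclusion after open allocation is the one risk that arithmetic cannot remove. Defining the set by mifepristone intake would not remove it either, because intake also follows allocation. A count of exclusions by group and reason in the trial report would show it.

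**Conclusion.** No change follows. This is missing detail that analysts would fill sensibly: treated women with a known outcome, compared by assigned group, with a stricter per-protocol set beside it. On that reading the planned 754 per group keep at least 90% power up to about 6.5% untreated by the corrected method, or 16% uncorrected, on top of the full 10% loss. The two analyses would seldom disagree, in about 3% to 5% of trials when the groups are truly equal.

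The conclusion assumes 97.5% efficacy in treated women, untreated shares that are modest and similar in both groups, and per-protocol departures unrelated to outcome. The documents give no rates for any of these shares. One section of the protocol was not available for review, so the absence of definitions is established only for the text at hand.
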